6.2.8 Multiple measurements

Here, a multiple measurement refers to a combination of analysis visit and timepoint where there are more than one value recorded for a given parameter.

Unless otherwise specified, if there are multiple measurements for a given parameter-visit-timepoint combination, values from the measurement that was performed last will be used.

For 12-lead ECG parameters (specifically, all parameters in the ADEG dataset), the mean value of all multiple measurements will be used for parameters measured quantitatively. For parameters measured qualitatively, the most severe value will be used.

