7.9.3 Laboratory values

Protocol-specified laboratory safety variables will be evaluated using descriptive statistics, line plots, and shift plots, showing the baseline value and post baseline values up to the end of treatment. Frequencies of normal and abnormal (low and high) laboratory findings will be summarised based on reference ranges provided for each analyte, and clinical significance of the findings will be evaluated.

Results from additional laboratory variables that were not specified in the protocol will not be summarised, but will appear in patient data listings.

A listing of patients fulfilling Hy's law criteria will be provided. That is, patients meeting all of the following criteria at a given visit:

1. Aspartate or alanine transaminase (AST, ALT) $\geq 3x$ the upper limit of normal (ULN)
2. Serum alkaline phosphatase $< 2x$ ULN
3. Bilirubin $\geq 2x$ ULN

Ratios of AST and ALT to ULN will be plotted against ratios of bilirubin to ULN for all subject-visits. Comparisons of both AST and ALT to the thresholds of $> 2, 3, 5,$ and 10 times their respective ULN will be summarised.

Renal impairment status will be determined from creatinine clearance (eGFR) (NICE) (Unwin et. al, 2011):

- Normal: ≥ 90 mL/min
- Mild reduction: 60 to 89 mL/min
- Mild to moderate reduction: 45 to 59 mL/min
- Moderate to severe reduction: 30 to 44 mL/min
- Severe reduction: 15 to 29 mL/min
- Kidney failure / End stage renal disease: < 15 mL/min

Hepatic impairment status will be determined as:

- Normal: Total bilirubin and AST \leq ULN
- Mild hepatic impairment: Total bilirubin $>$ ULN to $1.5 x$ ULN or (Total bilirubin \leq ULN and AST $>$ ULN)
- Moderate impairment: Total bilirubin $>$ 1.5 to $3 x$ ULN, any AST
- Severe impairment: Total bilirubin $>$ $3 x$ ULN, any AST

Additionally, descriptive statistics of the following categorised analytes will be reported:

Renal impairment thresholds based on creatinine levels in the blood (CTCAE v5.0):

- Grade 1: > ULN–1.5 x ULN
- Grade 2: > 1.5–3.0 x baseline or > 1.5–3.0 x ULN
- Grade 3: > 3.0 x baseline or > 3.0–6.0 xULN
- Grade 4: > 6.0 x ULN

Low potassium levels (hypokalemia) in blood (Unwin et al, 2011; Castro, 2019):

- Mild: 3 to 3.4 mmol/L
- Moderate: 2.5 to < 3 mmol/L
- Severe: < 2.5 mmol/L

Haemoglobin levels in blood (WHO, 2011):

- Non-pregnant women:
 - Mild: 110–119 g/L
 - Moderate: 80–109 g/L
 - Severe: < 80 g/L
- Pregnant women:
 - Mild: 100–109 g/L
 - Moderate: 70–99 g/L
 - Severe: < 70 g/L
- Men:

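### The Hy's law listing pairs liver values only within one visit, so a subject whose bilirubin reaches 2x ULN only after AST and ALT have fallen below 3x ULN is not listed

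*SAP*

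**What the plan says.** SAP 7.9.3 provides a listing of "patients meeting all of the following criteria at a given visit". The criteria are AST or ALT at least 3x ULN, ALP below 2x ULN and bilirubin at least 2x ULN. The accompanying graph uses the same unit: "Ratios of AST and ALT to ULN will be plotted against ratios of bilirubin to ULN for all subject-visits". The section also summarises AST and ALT against 2, 3, 5 and 10 times ULN, without saying whether by visit or by subject.

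SAP 6.2.8 covers repeats. There, "a multiple measurement refers to a combination of analysis visit and timepoint where there are more than one value recorded for a given parameter". The default for such repeats is that "values from the measurement that was performed last will be used". The only exception is for ECG: "For 12-lead ECG parameters (specifically, all parameters in the ADEG dataset), the mean value of all multiple measurements will be used" for quantitative parameters, and the most severe value for qualitative ones. Neither 6.2.8 nor 7.9.3 has a separate rule for laboratory values. Neither says how unscheduled samples are assigned to analysis visits.

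Protocol 6.5.6 allows control assessments after abnormal laboratory findings, so repeats are foreseen. Under protocol 4.5 and 6.1.6, subjects who stop study drug but stay in the study are followed for ALSFRS-R, ventilatory support and survival. Their planned laboratory assessment after stopping is the end-of-study visit, 14-25 days after the last dose.

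**The concern.** The listing is meant to bring rare, serious liver injury to case review, so a missed subject is the costlier error. Two features can remove one.

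- **Timing.** If bilirubin rises after the transaminases have come down, the two halves of one episode fall at different visits and are never put together. This could happen when a raised AST or ALT leads to stopping and bilirubin is raised only at the end-of-study visit. SAP 7.9.3 also shows laboratory values only up to the end of treatment in its descriptive displays, and does not say whether the Hy's law listing includes the end-of-study sample.
- **Repeats.** If a normalising control sample shares the analysis visit and timepoint of the abnormal one, the abnormal value is dropped before the criteria are checked. The AST and ALT threshold summaries would lose it too if they are built on the retained record.

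**Working it through.** The plan gives no figure to reproduce. The check has two parts: what the rule does, and how much the timing restriction could matter.

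**1. The rule applied to illustrative subjects.** The laboratory values are my assumptions, in multiples of ULN, with ALP at 1x throughout. The SAP rule keeps the last record per analysis visit and then requires all three criteria at one visit. The comparators are a check of every record, and a pairing of AST or ALT at least 3x with bilirubin at least 2x within the next 30 days (the 30 days is also assumed).

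| Subject | Values | SAP rule | Every record | 30-day pairing |
|---|---|---|---|---|
| A | Week 4: AST 4, ALT 5, bilirubin 2.5 | listed | listed | listed |
| B | Week 4: AST 4, ALT 5, bilirubin 1.2; Week 8: AST 2, ALT 2.5, bilirubin 2.5 | **not listed** | **not listed** | listed |
| C | Week 4: AST 6, ALT 8, bilirubin 1.2; Week 8: AST 3.2, ALT 4, bilirubin 2.5 | listed | listed | listed |
| D | As A, then a repeat four days later in the same analysis visit: AST 1.5, ALT 2, bilirubin 1.4 | **not listed** | listed | listed |
| E | As D, but the repeat is kept as its own unscheduled visit | listed | listed | listed |

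B and C show that the order of the peaks does not decide the matter. What decides it is whether AST or ALT is still at least 3x ULN when bilirubin is raised. D and E show that the repeat matters only through visit assignment. Checking every record repairs D but not B.

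**2. Size of the timing loss.** From the protocol's schedule of study events, planned visits fall on days 15, 29, 57, 85, 169, 253 and 337, with gaps of 14, 28, 28, 84, 84 and 84 days. Assumptions: end-of-study on day 355 (18 days after day 337, inside the 14-25 day window), uniform onset, no control samples, and ALP below 2x ULN. The cross-visit rule counts bilirubin at the same visit as AST or ALT, or later.

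Worked case: ALT raised for 28 days from onset t, bilirubin raised from t+21 to t+49, onset on days 1-85 (84 days).

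- Same-visit: a visit must fall in t+21 to t+28, so t lies in 1-8, 29-36 or 57-64. That is 21/84 = 25%.
- Cross-visit: every onset on days 1-64 has a visit in each window. After day 64 no visit falls in the bilirubin window. That is 63/84 = 75%.

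For the same course with onset on days 85-337 (252 days):

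- Same-visit: t lies in 141-148, 225-232, 309-316 or 327-334, which is 28/252 = 11%.
- Cross-visit: t lies in 141-148, 225-232 or 309-334, which is 39/252 = 15%.

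Other assumed courses, worked the same way:

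| ALT raised | Bilirubin raised | Early onset: same v cross | Late onset: same v cross |
|---|---|---|---|
| 4 weeks | from day 21, 4 weeks | 25% v 75% | 11% v 15% |
| 4 weeks | from day 14, 4 weeks | 50% v 83% | 21% v 22% |
| 6 weeks | from day 21, 6 weeks | 58% v 75% | 32% v 32% |
| 4 weeks | from day 7, 4 weeks | 75% v 92% | 28% v 28% |
| 4 weeks | from day 7, 3 weeks | 75% v 75% | 28% v 28% |

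The early loss runs from 0 to 50 points, and the late loss from 0 to about 4. These figures cover the timing restriction only; the last-value rule is not modelled.

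**The case against.** The SAP's definition is explicit and programmable, and it serves a descriptive listing with no hypothesis attached. Requiring concurrence buys specificity, and nothing in the documents says a later bilirubin rise must count. The listing does not stand alone. There are AST and ALT threshold summaries, frequencies of abnormal values with clinical significance, a hepatic AESI group counted to 25 days after the last dose, case-by-case SAE review with narratives, investigator review of all laboratory results, and DSMB safety meetings about every two months. Protocol 1.3.2 names no hepatic signal for oral levosimendan. The percentages come from injury courses found in neither document.

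All of this stands as a limit on the point. It also rules out four stronger readings that a reader might infer:

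- That every case whose bilirubin peaks after its transaminases is missed. Subject C is listed.
- That any repeat sample erases the abnormal one. That needs the same analysis visit and timepoint, and the SAP leaves the assignment open.
- That this listing is the trial's only liver screen. It is one of several outputs.
- That a fixed share of cases is lost. The share moves from nothing to half with the assumed course.

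The objection does not supply a planned output that joins a transaminase elevation to a later bilirubin elevation. The threshold summaries leave bilirubin out, the AESI group depends on what was reported as an adverse event, and the plot shows the two halves of a split case as unconnected points.

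**Conclusion.** The point holds in a limited form. As written, the SAP does not list a subject whose bilirubin is at least 2x ULN only at visits where AST and ALT are below 3x ULN. It may also fail to list a subject whose same-visit repeat has fallen, depending on an assignment rule it does not state. The size cannot be fixed from the documents. Under the assumed courses the timing loss is at most 50 points for onset in Weeks 0-12. It is little or nothing after Week 12, where the 84-day gaps cause most misses under either rule. No efficacy result, alpha or patient management is affected. This is a worthwhile, inexpensive improvement to safety reporting.

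**What to change.** 1. Keep the same-visit listing, but evaluate it on every post-baseline sample, scheduled or unscheduled, through the end-of-study visit, and state how unscheduled samples are assigned to analysis visits.
2. Add a review listing of subjects with any AST or ALT at least 3x ULN and any bilirubin at least 2x ULN at the same time or later, within a pre-specified pairing window, showing dates and ALP. The documents give no window, so the sponsor must choose one. Without one, a Week 2 ALT could be paired with an unrelated Week 48 bilirubin.
3. Add a plot of each subject's peak values.
4. Use the worst rather than the last value in the liver-test threshold summaries.

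The review listing should supplement the same-visit listing and pair any qualifying values. A rule that requires the highest bilirubin to come at or after the highest ALT would drop a subject with ALT 4x and bilirubin 3x at one visit and ALT 6x and bilirubin 2.2x at the next. With ALP below 2x ULN, the SAP lists that subject at both visits.

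The cost is SAP wording, minor programming on data already collected, and a few extra subjects to review who turn out not to be cases.

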5.3.2 Dose adjustment

The daily doses of oral levosimendan will be 1-2 mg depending on the tolerability (mainly judged by HR). The subjects will start with a 1 mg dose (in the morning) for 2 weeks.

HR will be assessed in the morning before study drug intake:

- At visit 2 (2 weeks):
 - If the HR in the 12-lead ECG has increased ≤ 15 bpm from baseline, the subject will increase the dose to 1 mg b.i.d.
 - If the HR in the 12-lead ECG has increased > 15 bpm from mean baseline value, the subject will continue with the 1 mg once daily. If the increase in HR is > 30 bpm in 3 separate recordings, the subject must discontinue the study treatment (see section 4.5).

- At visit 3 (4 weeks) or later visits:
 - If the HR in the 12-lead ECG has increased ≤ 20 bpm from baseline, no changes to the dosing regimen are made.
 - If the HR in the 12-lead ECG has increased > 20 bpm from baseline in 3 separate recordings taken within 5-10 minutes from each other, the subject will decrease the dose back to 1 mg once daily if treated with 1 mg b.i.d. In case the increase in HR is > 30 bpm in each of the 3 separate ECG recordings, the HR must be checked again at an additional visit approximately 2 weeks after the dose decrease. If the increase > 30 bpm is recorded at the dose level of 1 mg once daily in 3 separate recordings, the subject must discontinue the study treatment (see section 4.5).

Administration of placebo (1 or 2 capsules per day) will be based on the same criteria as described for levosimendan above.

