6.5.4 Clinical safety assessments

Vital signs (HR, systolic and diastolic BP) and standard 12-lead ECG will be assessed at screening, at each visit during the treatment period before and 30-90 minutes after the morning dose of the study drug, and at the end-of-study visit. At baseline visit, vital signs and ECG will be assessed before and 45-120 minutes after the morning dose of the study drug.

At the screening visit, only supine HR and BP will be measured. At baseline visit, each visit during the treatment period and end-of-study visit, supine HR and BP will be assessed after a 5-minute rest. Subjects will then be asked to stand up and after 3 minutes, standing HR and BP will be measured (orthostatic test). In case the subject is not able to stand, only supine HR and BP will be measured.

A standard 12-lead ECG (central reading) will be recorded with subject lying supine and after a 5-minute rest. 3 baseline recordings of ECG in 1-3 minutes intervals will be done before dosing at visit 1 (baseline). The HR, RR, PR and QT intervals and QRS duration will be analysed in the central ECG laboratory. QTc will be calculated using both Bazett's and Fridericia's correction. Each ECG will be assessed as normal/abnormal by the central ECG laboratory. Clinical significance of the abnormalities will be assessed by the investigator.

DNO 090017ff823c9bac / 1.0 Approved 40 / 58

Additional 1-2 assessments of 12-lead ECG should be performed within 5-10 minutes from each other (all before the morning dose), if the HR in the first recording was increased from baseline (visit 1) as follows:

- > 20 bpm if the subject is receiving the study treatment 1 mg b.i.d., to assess the need for dose reduction (see section 5.3.2)
- > 30 bpm if the subject is receiving the study treatment 1 mg once daily, to assess the need for discontinuation (see section 4.5)

If the HR increase is not repeated in the second ECG, no further ECG recordings are needed.

Physical examination will be performed at screening and the end-of-study visit. Weight will be measured at screening, at visits 1, 3, 4, 5, 6, 7, 8 and at the end-of-study visit. Height will be recorded at screening only.

In case there are abnormal findings, control assessments can be performed according to the judgement of the investigator.

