 - Mild: 110–129 g/L
 - Moderate: 80–109 g/L
 - Severe: < 80 g/L

Haematocrit levels in blood (Cohen et al, 2017):

- Women:
 - Low: < 37%
 - High: > 47%
 - Normal: 37% to 47%
- Men:
 - Low: < 42%
 - High: > 52%
 - Normal: 42% to 52%

Erythrocytes count in blood (Dean, 2005):

- Women:
 - Low: < $3.5 \times 10^{12}/L$
 - High: > $5.5 \times 10^{12}/L$
 - Normal: $3.5\text{--}5.5 \times 10^{12}/L$
- Men:
 - Low: < $4.3 \times 10^{12}/L$
 - High: > $5.9 \times 10^{12}/L$
 - Normal: $4.3\text{--}5.9 \times 10^{12}/L$

7.9.4 12-lead ECG

Descriptive statistics of standard 12-lead ECG variables and abnormal ECG findings will be tabulated by treatment group for each study visit.

QT values will be corrected (QTc) according to Bazett's (QTcB) and Fridericia's (QTcF) formulae. Disjoint comparisons of QTc values to the following thresholds will be summarised:

1. Absolute values > 450 ms, > 480 ms, and > 500 ms.
2. Changes from baseline > 30 ms, and > 60 ms.

Cardiac safety will be assessed by modelling the dose-response of post-dose OR-1896 concentration vs. $\Delta\Delta\text{QTcF}$ at each visit with PK samples. $\Delta\Delta\text{QTcF}$ is defined as the difference between change from baseline between placebo and treatment, where the placebo effect is estimated for each visit with an ANOVA model.

Disjoint comparisons of Masterscope heart rate (EGHRMS) changes from baseline to the protocol-defined thresholds of > 20 bpm and > 30 bpm will be summarised by treatment group, visit, and dose level at the visit.

For subjects whose dose-level is increased at Week 2, changes in Masterscope heart rate between the measurements taken before dosing at the Week 2 and Week 4 visits will be described.

For subjects whose dose-level is reduced, changes in Masterscope heart rate between the last measurement on the higher dose and the following measurement on the lower dose will be described.

The correlation between OR-1896 concentration and post-dose Overread heart rate (EGHROR) will be described with semi-log scatterplots at each study visit.

Drug-drug interactions with medications known to affect QT interval (see 7.10.1) will be evaluated for QT, QTcF and QTcB with descriptive statistics.

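### SAP 7.9.4 measures heart-rate change after a heart-rate-triggered dose reduction from the readings that caused it, so part of the described fall is regression to the mean

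*SAP*

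**What the plan says.** SAP 7.9.4 contains two descriptions of heart rate across a dose step.

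- **Step down.** It opens "For subjects whose dose-level is reduced, changes in Masterscope heart rate between the last measurement on the higher dose" and ends "and the following measurement on the lower dose will be described". It names no treatment group, no pre- or post-dose timepoint and no reason for reduction.
- **Step up.** It opens "For subjects whose dose-level is increased at Week 2, changes in Masterscope heart rate" and compares the Week 2 and Week 4 values. This item does specify readings before dosing.

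The rules that decide who enters these tables are in the protocol.

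- Section 5.3.2, for visit 3 onwards: the trigger is a heart rate that "has increased > 20 bpm from baseline in 3 separate recordings taken within 5-10 minutes from each other". Anyone then taking two capsules a day returns to one.
- Section 6.5.4: the repeat ECGs are "all before the morning dose".
- Section 5.3.2, at visit 2: only subjects whose heart rate has risen by at most 15 bpm step up. Placebo subjects follow the same criteria.
- Section 1.2.2 and the notes to Figure 1: the dose may also be lowered for other reasons.

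SAP 6.2.8 settles which number is used when an ECG is repeated at one timepoint: "the mean value of all multiple measurements will be used for parameters measured quantitatively".

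**The concern.** Taken together, these rules make the selecting value and the starting value the same for a heart-rate-triggered reduction. The last higher-dose measurement is the mean of the three recordings that triggered the step. A value picked because it is high is followed, on average, by a lower one. Repeating the ECG within minutes does not prevent this, because the repeats share whatever raised heart rate that morning.

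The step-up table is selected the other way. Subjects above 15 bpm at Week 2 are left out, so the rest tend to read somewhat higher at Week 4 whatever the dose does.

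Heart rate is the main tolerability measure behind dosing in this trial, and SAP 7.11 drops the mixed models for vital signs and ECG. These two items are then the only planned within-subject descriptions of heart rate across a dose step. A study report could present a predictable statistical fall as a response to the lower dose.

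**Working it through.** The plan states no figure for this analysis, so there is none to reproduce. The check asks what the tables would show if the dose step had **zero** effect on heart rate.

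**Inputs from the documents**
- Trigger: three same-visit readings all more than 20 bpm over baseline (Protocol 5.3.2).
- Step-up gate: Week 2 rise of at most 15 bpm (Protocol 5.3.2).
- Starting value: mean of the repeats (SAP 6.2.8).
- Mean rise on drug: 6-8 bpm. Protocol 1.1 gives about 8 bpm over placebo in both dose groups of the heart-failure study, and 6-8 bpm for 0.5-2 mg daily in the stroke/TIA study.
- Group sizes: about 300 and 150 (SAP 5).

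**Assumed, not in the documents**
- SD of the change from baseline 8-10 bpm, between-visit correlation 0.5-0.7, and a further SD of 2.5 bpm for a single reading.

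**Hand check** (mean rise 8, SD 9, correlation 0.6)
- Persistent variance: 0.6 × 81 = 48.6.
- Variance of a three-reading mean: 81 + 2.5²/3 = 83.08.
- Slope of a later visit on that mean: 48.6/83.08 = 0.585.
- Take an illustrative triggering mean of 24 bpm. Expected next value: 8 + 0.585 × (24 − 8) = 17.4. Fall: 24 − 17.4 = **6.6 bpm**.
- Now add the Week 2 gate. The variance of one Week 2 reading is 81 + 6.25 = 87.25. With both values as predictors, the determinant is 83.08 × 87.25 − 48.6² ≈ 4,887.
- Slope on the triggering mean: 48.6 × (87.25 − 48.6)/4,887 = 0.384. Slope on the Week 2 reading: 48.6 × (83.08 − 48.6)/4,887 = 0.343.
- For an illustrative Week 2 rise of 10 bpm, the expected next value is 8 + 0.384 × 16 + 0.343 × 2 = 14.8. Fall: **9.2 bpm**.

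The gate increases the artefact. A subject known to have been at or below 15 bpm at Week 2 has less persistent elevation to explain a reading above 20.

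**Simulation of the protocol rule.** The gate applies at Week 2 and triggers can occur at Weeks 4, 8, 12, 24 and 36. Week 48 is left out because no on-treatment reading follows it.

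| Quantity, with no effect of the dose step | Expected value |
|---|---|
| Triggered reduction, change from triggering mean, levosimendan | about −8.5 to −13 bpm |
| Same change, levosimendan minus placebo | about +1 to +3 bpm |
| Change from last pre-trigger visit, reduction at Week 8 or later | about +0.7 to +1.7 bpm |
| Change from previous visit, reduction at Week 4 | about +4 to +6 bpm |
| Week 2 to Week 4 change in those stepping up | about +1 to +2 bpm |
| Triggered placebo reductions, of 150 | about 1-6 |

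Reductions at Week 4 make up about a quarter of the simulated reductions.

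**Second variance model.** This one used visit-to-visit SD 4, 6 or 8, within-visit SD 2 or 4, between-subject SD of the drug effect 3 or 6, and mean rise 8.
- Levosimendan: −7.6 to −13.7 bpm, with 8-47 triggered reductions of 300.
- Placebo: −11.7 to −16.5 bpm, with 0.1-10 triggered reductions of 150.
- Using the third reading instead of the mean of three changed the result by at most 0.1 bpm.
- Placebo again regresses more. In one scenario the difference is −8.4 − (−11.7) = +3.3 bpm.

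**The case against.** The strongest reply is that nothing is being inferred. The SAP only describes the changes: there is no test, no estimated dose effect and no claim that the lower dose helps. A reader might infer that the plan intends to credit the fall to the lower dose, but the documents do not say so. That stands, and it limits the point to how a safety table will be read.

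Further replies, and what remains of each:

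- **The table is not only triggered reductions.** This stands. Reductions for other reasons are pooled in, are not selected on high heart rate, and dilute the artefact by an unknown amount.
- **Dose and heart rate are examined elsewhere.** SAP 7.9.4 also summarises threshold exceedances by treatment group, visit and dose level, and plots concentration against heart rate. A population PK/PD model covering heart rate is an exploratory objective. These analyses give context, but none follows a subject across a dose step.
- **Silence on treatment group is not a plan to pool.** This is fair, since SAP 7.9.4 opens with ECG tabulations by treatment group. The wording should still settle it.
- **The starting reading might be post-dose.** The step-down item names no timepoint. A post-dose reading at the same visit would still share that day's elevation, and could add a pre/post-dose mismatch.
- **The SDs and correlations are assumed.** This stands for the size. The direction does not depend on them.

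**Conclusion.** The point holds for heart-rate-triggered reductions. The change is measured from the readings that selected the subject, so a fall is expected with no effect of the dose step. Its size is roughly 8-13 bpm if the change SD is 8-10 and the between-visit correlation 0.5-0.7. That is as large as the 6-8 bpm mean rise in Protocol 1.1. The step-up table has an artefact of about +1 to +2 bpm, which overstates the rise.

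Three stronger readings are tempting and not supported.

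- **The whole reduction table would show a fall of 8-13 bpm.** It mixes reasons for reduction, and the mix is not known in advance.
- **Any observed fall is pure artefact.** A real effect of the lower dose may be present; the table as written cannot separate the two.
- **Subtracting placebo removes the problem.** Triggered placebo subjects start from a lower mean and regress further. The difference is itself biased by about +1 to +3 bpm under the main assumptions, and it rests on perhaps 1-6 placebo subjects.

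No efficacy endpoint, error rate or sample size is affected. This is a low-cost improvement to a descriptive safety output.

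**What to change.** Revise the two items in SAP 7.9.4 as follows.

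1. Present both tables by treatment group.
2. Split reductions into heart-rate-triggered and other reasons. SAP 6.2.14 already identifies dose changes related to heart-rate increase, so the split is feasible.
3. Use pre-dose readings for both values in the step-down table, as the step-up item already does.
4. For triggered reductions at Week 8 or later, add the change from the last pre-trigger visit on the higher dose. Leave Week 4 reductions out of this row: their previous visit was on 1 mg once daily and was itself selected at 15 bpm or less.
5. Footnote that regression to the mean is expected in the change from the triggering reading, and that the step-up table has a smaller selection effect.
6. Do not present levosimendan minus placebo as the corrected estimate. The placebo column is for display only.

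The cost is SAP wording and a few extra table rows, with no new data and no change to the dosing rule or trial conduct. Some cells will be small and imprecise, and the added row keeps a residual artefact of about +0.7 to +1.7 bpm.
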